#### **4.3 TREATMENT COMPLIANCE**

Assessment for compliance will be conducted using pill counting at the end of each cycle. Remaining pills at the end of the cycle will be noted in the patient's research chart and discarded prior to provision of study drug for the subsequent cycle. A pill diary will be used and completed by the study nurse after each cycle.

### **5. VARIABLES AND THEIR ASSESSMENT**

#### **5.1 EFFICACY**

##### **5.1.1 End point(s) of efficacy**

The first portion of this trial which aimed to determine PFS3 in an unselected population of urothelial cancer patients has been fully accrued, analyzed, and published. Based on those data, the below end points reflect those of the new amendment for this study.

##### Primary endpoint:

To determine the 6-month PFS rate of molecularly-selected metastatic urothelial cancer patients treated with afatinib who have progressed despite prior platinum-based chemotherapy.

Radiographic assessment of responses will be performed via CT or MRI every 8 weeks until disease progression is observed or until drug intolerance.

##### Secondary endpoints:

To determine the overall response rate (CR + PR), median progression free survival, and overall survival for the same treated population.

To examine the role of different *ErbB* alterations in determining afatinib activity in urothelial cancer.

##### Exploratory Endpoints:

To determine the PFS6 rate, overall response rate, and OS among the predefined subset of patients with qualifying alterations exclusive of *EGFR* alterations.

To determine whether tumor *EGFR* and/or *HER2* expression, or, alternatively, whether certain microRNAs, influence 6-month PFS in patients treated with afatinib.

This exploratory endpoint is based on the hypothesis that the level of *EGFR* and/or *HER2* expression may influence drug activity. One study which required expression of either *EGFR* or *HER2* prior to enrollment examined the variability of these markers in patients with refractory advanced/metastatic urothelial cancer. For *EGFR*, the respective percentages of patients with each expression quartile were 12% (0), 35% (1), 33% (2), and 19% (3). For *HER2*, the quartile percentages were 23% (0), 32% (1), 37% (2), and 7% (3). Notably, 71%

of patients had high overexpression (defined as 2+ or 3+) of at least one of the targets. Additionally, 22% of patients had high co-overexpression (2+ or 3+ for both EGFR and HER2). The method used for quantifying expression will follow standard commercially developed assays.

Alternatively, studies have suggested that epithelial-to-mesenchymal transition, a cellular development process that is associated with cellular invasion and migration, may confer resistance to EGFR-directed therapy. Specifically, in cell line models, expression of the microRNA miR-200 has been shown to induce mesenchymal-phenotype bladder cancer cells to adopt a phenotype resembling their epithelial counterparts, and to simultaneously increase sensitivity to EGFR inhibition. We will therefore consider evaluation of tumor tissue for determination of whether tumor microRNAs like miR-200 have bearing on the 6-month PFS in this study.

Finally, RNA profiling of available tissue may be performed if technically feasible. On a DNA level, specific genomic alterations may be confirmed/investigated post-hoc for scientific purposes (not for eligibility purposes), and overall mutational profiling may be assessed.

### **5.1.2 Assessment of efficacy**

## **5.2 SAFETY**

### **5.2.1 Endpoint(s) of safety**

Safety of afatinib will be evaluated as indicated by intensity and incidence of adverse events, graded according to US NCI CTCAE Version 4.0. Safety endpoints include:

- events leading to dose reduction
- events leading to permanent treatment discontinuation
- the overall incidence and CTC criteria grade of adverse events, as well as relatedness of adverse events to treatment
- causes of death

### **5.2.2 Assessment of adverse events**

#### **5.2.2.1 Definitions of adverse events**

##### **Adverse event**

An adverse event (AE) is defined as any untoward medical occurrence, including an exacerbation of a pre-existing condition, in a patient in a clinical investigation who received a pharmaceutical product. The event does not necessarily have to have a causal relationship with this treatment.

##### **Serious adverse event**

A serious adverse event (SAE) is defined as any AE which results in death, is immediately life-threatening, results in persistent or significant disability/incapacity, requires or prolongs patient hospitalization, is a congenital anomaly/birth defect, or is to be deemed serious for any other reason if it is an important medical event when based upon appropriate medical

judgement which may jeopardize the patient and may require medical or surgical intervention to prevent one of the other outcomes listed in the above definitions.

#### Serious and Unexpected Suspected Adverse Reaction (SUSAR)

A serious adverse event is considered to be a suspected adverse reaction (SAR) if there is evidence to suggest a causal relationship to the study agent. This may include a single occurrence of an event strongly associated with drug exposure (e.g. Stevens-Johnson Syndrome), one or more occurrence of an event otherwise uncommon in the study population, or an aggregate analysis of specific events occurring at greater frequency than expected.

Unexpected events are those not listed at the observed specificity or severity in the listed adverse event section of the investigator brochure for the product.

ALL SUSARS occurring on this clinical trial must be reported to the FDA by the University of Chicago/IND Holder. Participating institutions that are not the University of Chicago will report SUSARS to the University of Chicago who will then report to the FDA. Refer to Sections 5.2.2.2 - 5.2.2.3 for full reporting guidelines.

#### Intensity of adverse event

The intensity of adverse events should be classified and recorded according to the Common Terminology Criteria for Adverse Events (CTCAE) version 4.0 in the University of Chicago CRF (eVelos system).

#### Causal relationship of adverse event

Medical judgment should be used to determine the relationship, considering all relevant factors, including pattern of reaction, temporal relationship, de-challenge or re-challenge, confounding factors such as concomitant medication, concomitant diseases and relevant history. Assessment of causal relationship should be recorded in the case report forms.

Yes: There is a reasonable causal relationship between the investigational product administered and the AE.

No: There is no reasonable causal relationship between the investigational product administered and the AE.

#### Worsening of the underlying disease or other pre-existing conditions

Worsening of the underlying disease or of other pre-existing conditions will be recorded as an (S)AE in the (e)CRF.

#### Changes in vital signs, MUGA, physical examination, and laboratory test results

Changes in vital signs, MUGA, physical examination and laboratory test results will be recorded as an (S)AE in the (e)CRF, if they are judged clinically relevant by the investigator.

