### **1.2.2 Clinical pharmacokinetic and safety**

PK data available from clinical trials until now indicate that afatinib was moderately fast absorbed after oral administration, with median  $t_{max}$  values mainly between 1 and 6 hours. For afatinib there was no deviation from dose-proportionality detectable. However, moderate to high inter- and intra-individual differences in plasma concentrations were seen. Afatinib was highly distributed out of the blood and had a moderate to high clearance. The mean terminal half-life was mainly in the range of 13-57 h. Steady state was reached no later than 8 days after the first administration. The major route of elimination of afatinib was via the faeces. After food intake, a decreased systemic exposure was observed compared to administration of afatinib under fasted conditions. Therefore, afatinib should be taken without food (i.e. afatinib should be taken at least 1 hour before or at least 2 hours after a meal). Typically, an accumulation ratio based on AUC values between 1.8 and 4.0 has been observed. At doses of 40 mg and above individual  $C_{max,ss}$  and  $AUC_{t,ss}$  values were mainly in the same range as those found to demonstrate anti-tumor activity in nude mouse tumor xenograft models.

Adverse events observed with afatinib are consistent with those reported for other EGFR inhibitors and include predominantly gastrointestinal (GI) and dermatological AEs which are dose-dependent. Diarrhea usually occurred within the first 2 weeks of treatment. Grade 3 diarrhea most frequently occurred within the first 6 weeks of treatment. Patients of low body weight, females, and patients with low baseline renal function appear to be at increased risk for developing Grade 3 diarrhea. A small number of patients experienced dehydration and prerenal insufficiency, most likely secondary to GI AEs, particularly diarrhea.

Rash/acne occurs at a high frequency; with half of the cases beginning within 4 weeks of exposure to afatinib. Those at higher risk for Grade 3 rash/acne appear to be the patients of low body weight/body surface area and patients with low baseline renal function.

Early, proactive, and effective management of these adverse events is mandated in ongoing and forthcoming clinical trials with early intervention to manage diarrhea and skin toxicities.

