**Table 4.1.3.2:1 Dose reduction/dose discontinuation scheme**

AE Type and grade	Action	Dose reduction/ discontinuation scheme
Grade 4 rash	Permanently discontinue afatinib	Permanently discontinue afatinib
Grade $\geq 3$ interstitial lung disease	Permanently discontinue afatinib	Permanently discontinue afatinib
Grade 4 hepatic impairment	Permanently discontinue afatinib	Permanently discontinue afatinib
Grade $\geq 3$ keratitis	Permanently discontinue afatinib	Permanently discontinue afatinib
Grade 2 left ventricular dysfunction (i.e., new resting ejection fraction of 40-50%; OR a 10-19% drop from baseline) 	Pause treatment with afatinib for 14 days and then repeat MUGA scan. If the ejection fraction has resolved to grade 1 or better at the time of the repeat MUGA, study drug will be resumed. If the toxicity has not resolved, afatinib should be permanently discontinued.	If patient was receiving 40 mg, resume treatment at 30 mg  . If patient was receiving 30 mg, resume treatment at 20 mg  . If patient was receiving 20 mg, discontinue afatinib.
Any symptomatic (grade $\geq 3$ ) left ventricular dysfunction 	Permanently discontinue afatinib	Permanently discontinue afatinib
CTCAE grade $\geq 2$ diarrhea persisting for 2 or more consecutive days (48 hours) despite adequate anti-diarrheal medication/hydration	Pause treatment with afatinib until toxicity has recovered to CTCAE grade $\leq 1$ or baseline  . If patient has not recovered to CTCAE grade $\leq 1$ within 14 days, study treatment should be permanently discontinued 	If patient was receiving 40 mg, resume treatment at 30 mg  . If patient was receiving 30 mg, resume treatment at 20 mg  . If patient was receiving 20 mg, discontinue afatinib.
CTCAE grade $\geq 2$ nausea and/or vomiting persisting for 3 or more consecutive days despite anti-emetic treatment/hydration		
CTCAE grade 2 or grade 3 worsening of renal function as measured by serum creatinine, newly developed proteinuria, or newly developed decrease in glomerular filtration rate of more than 50% from baseline		
CTCAE grade 4 worsening of renal function	Permanently discontinue afatinib	Permanently discontinue afatinib

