#### **5.2.4.2 Left ventricular function**

Left Ventricular Ejection Fraction (LVEF) as measured by Multi-Gated Acquisition Scan (MUGA) will be assessed at time points specified in the Flow Chart.

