### **7.1.3 Safety analyses**

Safety analyses can occur at any time deemed necessary by the lead investigator or the drug sponsor and must occur at the first interim analysis (29 patients) and at the end of the study. Adverse event rates will be summarized by type, grade, and attribution and descriptive statistics (frequency distributions) generated.

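### LVEF and laboratory changes that trigger no mandated action or report enter the safety analysis only on investigator judgment, and no analysis of the measured values is planned

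*Combined protocol and SAP*

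**What the plan says.** - **Recording.** Under section 5.2.2.1, changes in vital signs, MUGA, physical examination and laboratory results "will be recorded as an (S)AE in the (e)CRF, if they are judged clinically relevant by the investigator". No grade or cut-off is attached.
- **Endpoints.** Section 5.2.1 states: "Safety of afatinib will be evaluated as indicated by intensity and incidence of adverse events, graded according to US NCI CTCAE Version 4.0". The listed endpoints include "events leading to dose reduction" and "events leading to permanent treatment discontinuation", together with overall AE incidence, grade and relatedness, and causes of death.
- **Analysis.** Section 7.1.3 states: "Adverse event rates will be summarized by type, grade, and attribution and descriptive statistics (frequency distributions) generated". This is required at the 29-patient interim and at the end of the study. No laboratory shift table or LVEF summary is named.
- **Measurement.** LVEF "as measured by Multi-Gated Acquisition Scan (MUGA) will be assessed at time points specified in the Flow Chart" (section 5.2.4.2), and a Flow Chart footnote sets the interval at 12 weeks. The Flow Chart schedules chemistry every two weeks to week 12 and every four weeks after that.
- **Dose table.** Table 4.1.3.2:1 defines grade 2 left ventricular dysfunction as "new resting ejection fraction of 40-50%; OR a 10-19% drop from baseline", without requiring symptoms, and attaches a mandatory pause and repeat scan. Grade 2 to 4 renal worsening also carries mandatory action. Section 4.1.3.2 limits the table to treatment-related toxicity.
- **Hepatic rule.** Section 5.2.2.4 defines hepatic injury by AST or ALT above a multiple of ULN together with bilirubin above twice ULN in the same sample. It requires expedited reporting whether or not the event is serious.

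**The concern.** The trial measures LVEF and chemistry on a fixed schedule, but its planned safety output contains only what was recorded as an AE. For many measured changes, recording depends on a local judgment with no stated standard. Two sites could see the same creatinine or LVEF value and one could record it while the other does not. With a single open-label arm, no control group would reveal this.

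Organ toxicity is a concern in the plan itself. A first-cohort patient who had not progressed stopped treatment for depressed ejection fraction (Synopsis; section 2.2). Section 2.2 also notes unexpectedly frequent cardiac toxicity with another HER2-directed agent, and section 1.2.1 reports reduced contractility in minipigs and renal papillary necrosis in rats. A low reported rate of such abnormalities at the interim or final analysis could reflect non-recording as well as true absence, and the planned tables could not tell the two apart.

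**Working it through.** No published figure needs reproducing. The check is which measured changes have a route into the section 7.1.3 summary other than the relevance judgment of section 5.2.2.1.

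| Measured change | Other route | What the route depends on |
|---|---|---|
| LVEF in the grade 2 range | Table 4.1.3.2:1: pause and repeat scan, then reduced dose or discontinuation; feeds two endpoints of section 5.2.1 | Judged treatment-related |
| LVEF fall smaller than the grade 2 range | None | - |
| Asymptomatic LVEF fall beyond the grade 2 range | Neither cardiac row fits, since the other row is for symptomatic dysfunction; only the catch-all row for other drug-related AEs of grade 3 or above | Must already count as an AE and be judged related |
| Renal worsening, grade 2 to 4 | Table 4.1.3.2:1: pause then reduced dose or discontinuation (grade 2 or 3), or discontinuation (grade 4) | Judged treatment-related |
| Creatinine change below grade 2 | None, unless the table's proteinuria or GFR criterion is also met | - |
| Transaminases and bilirubin both above the section 5.2.2.4 limits | Mandatory expedited reporting | Measured values alone |
| Isolated transaminase rise | Below grade 3, no mandatory row; at grade 3, the catch-all row; grade 4 hepatic impairment has its own row | Catch-all row presupposes a related AE |
| Any of these judged unrelated | Section 4.1.3.2 allows an optional pause but no dose reduction | Does not reach the dose-reduction endpoint |

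Three points follow.

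1. The table directs dosing, not AE recording. Section 5.2.2.1 names MUGA explicitly and makes no exception for values inside the table's ranges. The two texts are compatible only if a reader assumes that a value leading to mandated action is always recorded.
2. Section 5.2.2.4 secures reporting, but section 7.1.3 plans no count of patients who meet its criterion.
3. The rows with no route, the rows that presuppose an AE and the changes judged unrelated make up the gap.

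On size, the number missed for one abnormality would be N × true rate × (1 − share recorded). The planned N is 72, but the documents give neither of the other two terms. What can be stated is the effect of one unrecorded patient: 1/72 = 1.4 percentage points at the end and 1/29 = 3.4 points at the interim. This takes the planned cohort sizes as denominators, since section 7.1.3 names none.

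**The case against.** The strongest reply is that the more important changes already have a route. A treatment-related grade 2 LVEF fall requires a pause and then a lower dose or discontinuation, so it should appear under dose reduction or discontinuation unless the dose table is disregarded. Grade 2 to 4 renal worsening is treated similarly, and combined hepatic elevation must be reported on laboratory values alone. All of this stands. A reader might infer that graded LVEF falls are never counted, or that every measured change depends on the relevance judgment. The documents do not support either reading.

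A second reply is that the cited history does not show non-recording. The first-cohort ejection-fraction case was detected and reported. The renal statement in section 1.2.2, "A small number of patients experienced dehydration and prerenal insufficiency, most likely secondary to GI AEs, particularly diarrhea", describes an effect that follows a clinically evident event, not a silent one. This also stands. These facts show that organ function matters here, not that cases were lost.

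A third reply is that section 8.1 provides for monitoring of data completeness and accuracy and a weekly multi-institutional safety review. That helps, but without a stated threshold a monitor has no standard for asking why a sub-threshold value was not recorded as an AE.

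Finally, no safety rate enters the decision rule of section 7.1.1. That is correct, and it limits how serious the point is.

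**Conclusion.** The point holds for a defined remainder: sub-threshold LVEF and creatinine changes, isolated transaminase rises, asymptomatic LVEF falls beyond the grade 2 range, and changes judged unrelated. For these, recording rests on an unstandardised judgment and no analysis of the measured values is specified. Reported abnormality rates can therefore be too low and can vary by site.

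This is a risk, not a demonstrated shortfall. A reader might be tempted to assume a true abnormality rate and a recording share and to quote a number of lost cases. Both inputs would be guesses, and applying them to all graded changes would ignore the mandated routes above. The documents do not allow the size to be calculated.

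The primary efficacy analysis is unaffected. The change should be made because the organ-toxicity description depends on it and it is inexpensive. The conclusion assumes that section 7.1.3 is the complete planned safety analysis.

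**What to change.** In section 7.1.3, keep the summary of investigator-recorded AEs and add beside it:

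- the worst post-baseline CTCAE v4.0 grade computed from the scheduled values of LVEF, creatinine, AST, ALT, bilirubin and electrolytes, as baseline-to-worst shift tables among patients with at least one post-baseline value, stating how many have none;
- LVEF change from baseline at each scan;
- a direct count of patients meeting the hepatic criterion of section 5.2.2.4.

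Confirm that these values are captured in eVelos. The data-reporting text in section 6.3.2 refers only to required data and does not say whether laboratory and MUGA values are included. Reconcile section 5.2.2.1 with Table 4.1.3.2:1 and section 5.2.2.4, so that the text states how the relevance judgment relates to values that trigger mandated action or reporting. No dose or clinical rule needs to change.

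The cost is a short text revision and a few extra tables, plus extraction from source records if the values are not in the database. Abnormality rates will look somewhat less favourable, and some of the derived grades will reflect measurement noise. Showing both summaries together lets the reader judge that.

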### **5.2.2.2 Adverse event and serious adverse event reporting**

Upon inclusion into the study, the patient's condition is assessed (e.g. documentation of history / concomitant diagnoses and diseases), and relevant changes from baseline are noted subsequently.

All adverse events, serious and non-serious, occurring during the course of the clinical trial (i.e., from signing the informed consent onwards through the 28 days follow-up period) will be collected, documented and reported to the sponsor by the investigator on the appropriate CRFs / SAE reporting forms (BI SAE report form or alternatively the CIOMS form/MEDWATCH form).

Serious Adverse Event reporting will be done according to the specific definitions and instructions detailed in Section 5.2.2.3 below.

For each adverse event, the treating investigator will provide the onset date, end date, CTC AE grade, treatment required, outcome, seriousness, and action taken with the investigational drug. The treating investigator will determine the relationship of the investigational drug to all AEs as defined in Section 5.2.2.1.

Adverse events with onset within first administration of afatinib therapy and 28 days after last administration of afatinib will be considered as on treatment. All AEs, including those persisting after end of study treatment must be followed up until they have resolved or have been sufficiently characterized or the principal investigator decides to not further pursue them.

Serious and non-serious adverse events occurring later than 28 days after last administration of trial drugs will only be reported in case they are considered drug-related or trial (procedure) related.

Deaths (unless they are considered drug-related or trial related) will not be reported as SAE when they occur later than 28 days after last administration of the trial.

### **5.2.2.3 Responsibilities for SAE reporting**

All SAEs occurring on this trial must be reported to the Study Chair/IND Holder, University of Chicago Comprehensive Cancer Center (UCCCC), and Boehringer Ingelheim Pharmaceuticals. Events meeting the additional reporting criteria noted below will be reported to the Institutional Review Board and/or the FDA as applicable.

#### **5.2.2.3.1 Reporting Events to the UCCCC**

All serious adverse events and protocol violations/ deviations must be reported to the UCCCC Cancer Clinical Trials Office (CCTO) in accordance with the UCCCC Data Safety Monitoring Plan.

All serious adverse events occurring on this study require expedited reporting to the University of Chicago Comprehensive Cancer Center (UCCCC) Clinical Trials Office (CCTO). The responsible Research Nurse or other designated individual at the treating site

should report the SAE to the CCTO by the end of the business day when s/he becomes aware of the event. Events occurring after business hours should be reported to the CCTO by 12pm (noon) the next business day. Reports should be made using the 'Serious Event Report' Form. Please scan and send via email (preferred) or FAX to:

University of Chicago Phase II CRA General  
[contact]  
[contact]  
[contact]

UC CCC Cancer Clinical Trials Office of Quality Assurance  
[contact]

All unexpected adverse reactions must be reported to both the IND holder and FDA. The responsible Research Nurse or other designated individual at the treating site should also provide a more complete written report using the FDA MedWatch 3500A form/CIOMS form. The completed form should be sent to the CCTO at [contact] and to the Phase II CRA at [contact], within the timelines specified below regardless of whether all information regarding the event is available. If applicable, a follow-up report should be provided to the CCTO if additional information on the event becomes available.

*Fatal or Life-threatening Events*: within 4 calendar days from treating investigator knowledge of the event

*All Other Reportable Events*: within 10 calendar days of treating investigator knowledge of the event

Participating sites should not forward any adverse event reports directly to the FDA. The UCCCC CCTO will report all events to the FDA as per the current FDA guidelines.

